9.2. Setting

This study will evaluate adult patients with RRMM who initiate elranatamab. Patients will enter (i.e., index) on the first observed elranatamab claim between 14 August 2023 and the end of data (defined as the latest data at the time of the specified analysis). Limited eligibility criteria will be applied.

Study Period: Start of data availability (01 January 2016) to the end of data

MM diagnosis window: Start of data availability (01 January 2016) to index date

Index date: First elranatamab claim after initial MM diagnosis

Observability: At least 180 days of continuous closed-claims medical and pharmacy enrollment prior to index (inclusive)

[figure not shown]
Baseline period for MM-related treatments and MM-related comorbidities: MM diagnosis to one day prior to index date (unless otherwise specified)

CCI and baseline HCRU assessment window: 180 days prior to index date to index date.

Follow-up: Index date until death, the earliest of the end of data, or end of continuous enrollment (unless otherwise noted). Alternative censoring criteria will be applied for certain outcomes (such as OS, TTD, and TTNT/D); see [Section 9.7](#) for more details.

Figure 1 reflects the time periods of interest in the study cohort.

Figure 1. Study Schematic for Patients Receiving Elranatamab

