1	Neutrophil count	Lab event with neutrophil as the test name and thousands/ μ L as the result units (dichotomous)	180 days prior to index date to index date
		Most recent numeric value to index date of a lab event with neutrophil count as the test name and thousands/ μ L result units (continuous)	
1	Creatinine	Lab event with creatinine as the test name and mg/dL as the result units (dichotomous)	180 days prior to index date to index date

Objective	Variable	Definition	Assessment Period(s)
		Most recent numeric value of a lab event to index date with creatinine as the test name and mg/dL as the result units (continuous)	
1	Hemoglobin	Lab event with hemoglobin as the test name and g/dL as the result units (dichotomous)	180 days prior to index date to index date
		Most recent numeric value of a lab event with hemoglobin as the test name and g/dL as the result units (continuous)	
1	Lymphocyte count	Lab event with lymphocyte count as the test name and thousand/ μ L as the result units (dichotomous)	180 days prior to index date to index date
		Most recent numeric value of a lab event with lymphocyte count as the test name and thousand/ μ L as the result units (continuous)	
1	Monocyte count	Lab event with monocyte count as the test name and thousand/ μ L as the result units (dichotomous)	180 days prior to index date to index date
		Most recent numeric value of a lab event with monocyte count as the test name and thousand/ μ L as the result units (continuous)	
1	Platelet Count	Lab event with platelet count as the test name and thousand/ μ L as the result units (dichotomous)	180 days prior to index date to index date
		Most recent numeric value of a lab event with platelet count as the test name and thousand/ μ L as the result units (continuous)	

Objective	Variable	Definition	Assessment Period(s)
1	Serum immunoglobulin A (IgA)	Lab event with IGA as the test name and mg/dL as the result units (dichotomous)	180 days prior to index date to index date
		Most recent numeric value of a lab event with IGA as the test name and mg/dL as the result units (continuous)	
1	Serum immunoglobulin G (IgG)	Lab event with IGG as the test name and mg/dL as the result units (dichotomous)	180 days prior to index date to index date
		Most recent numeric value of a lab event with IGG as the test name and mg/dL as the result units (continuous)	

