Exploratory Obj 1	ICANS ¹	Medical claim with an ICD-10 code in the IP, non-IP or pharmacy setting for CRS, categorized into the following grades (categorical): Any (all grades and unspecified grade) Grade 1 Grade 2 Grade 3 Grade 4 Grade 5 If patients have multiple, conflicting grades, then the highest recorded grade will be reported	Index date to end of follow-up, where follow-up will be based on last dose of elranatamab (eg, 14 days after last recorded dose or 90 days after last recorded dose). See Section 9.7.6 for censoring criteria
Hematologic events			
Exploratory Obj 1	Anemia ¹	Medical claim with an ICD-10 code in the IP, non-IP, or pharmacy setting for anemia or event in the lab table where hemoglobin is <10g/dL (dichotomous)	Index date to end of follow-up, where follow-up will be based on last dose of elranatamab (eg, 14 days after last recorded dose or 90 days after last recorded dose). See Section 9.7.6 for censoring criteria

Exploratory Obj 1	Neutropenia ¹	Medical claim with an ICD-10 code in the IP, non-IP, or pharmacy setting for lymphopenia or event in the lab table where lymphocyte count is < 1,000 per uL (dichotomous)	Index date to end of follow-up, where follow-up will be based on last dose of elranatamab (eg, 14 days after last recorded dose or 90 days after last recorded dose). See Section 9.7.6 for censoring criteria
Exploratory Obj 1	Lymphopenia ¹	Medical claim with an ICD-10 code in the IP, non-IP, or pharmacy setting for lymphopenia or event in the lab table where lymphocyte count is < 1,000 per uL (dichotomous)	Index date to end of follow-up, where follow-up will be based on last dose of elranatamab (eg, 14 days after last recorded dose or 90 days after last recorded dose). See Section 9.7.6 for censoring criteria
Non-hematologic events			
Exploratory Obj 1	Hypogammaglobulinemia ¹	Medical claim with an ICD-10 code in the IP, non-IP, or pharmacy setting for hypogammaglobulinemia or event in the lab table where IGG value is ≤ 400 mg/dL (dichotomous)	Index date to end of follow-up, where follow-up will be based on last dose of elranatamab (eg, 14 days after last recorded dose or 90 days after last recorded dose). See Section 9.7.6 for censoring criteria

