9.7.6. Tolerability

The prevalence and incidence for each AE (Table 3) will be estimated. All prevalence and incidence estimate will be reported as a percent with corresponding 95% CIs.

$$\text{Prevalence} = \left(\frac{\text{Number of patients with an event}}{\text{Total number of patients in the cohort}} \right) \times 100$$

For the incidence analysis, only patients who did not have the event in prior to their index date will be excluded. The length of the washout is dependent on the outcome (see Table 3).

$$\text{Incidence} = \left(\frac{\text{Number of patients with an event who did not have an event at baseline}}{\text{Total number of patients in the cohort}} \right) \times 100$$

Patients will be assessed over two time periods: from the index date until 14 days or 90 days after their last administration of the index medication.

Additionally, the time to infection onset will be assessed using unadjusted Kaplan-Meier methods. The median time to event in days will be reported along with the IQR. The 95% CIs for the median time to event will be calculated using log-log transformation.

Patients will be censored at the earliest of death, the end of continuous closed-claim coverage, the latest data at the time of the specified analysis, or next treatment (CAR-T, BsABs, bendamustine or belantamab).

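### An index-date hemoglobin, lymphocyte or IgG result is both the Table 2 baseline value and a qualifying Table 3 adverse event

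*Protocol*

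**What the plan says.** Section 9.2 of the protocol sets the anchor: "Index date: First elranatamab claim after initial MM diagnosis". Three sets of rules then refer to that day.

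- **Baseline laboratory values (Section 9.3, Table 2).** The assessment period is "180 days prior to index date to index date". Within it the rule for lymphocytes is "Most recent numeric value of a lab event with lymphocyte count as the test name"; hemoglobin and IgG follow the same rule. A result dated on the index date is therefore the one reported as baseline.
- **Adverse events (Section 9.3, Table 3, and Section 9.7.6).** The window is "Index date to end of follow-up, where follow-up will be based on last dose of elranatamab", ending 14 or 90 days after the last administration. Anemia is met by a diagnosis code or by an "event in the lab table where hemoglobin is <10g/dL". Lymphopenia (fewer than 1,000 per µL) and hypogammaglobulinemia (IgG of 400 mg/dL or less) are built in the same way. One result is enough; no change from baseline or confirmatory sample is asked for.
- **Washout.** The Table 3 footnote gives these events a 30-day washout for incident cases. Section 9.7.6 places it before the index date, in a garbled sentence about patients who "did not have the event in prior to their index date". The incidence formula then removes patients with an event at baseline, without defining baseline. Prevalence has no washout.

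**The concern.** The two windows share one day, and it is the day on which treatment is taken to start. A hemoglobin of, say, 9.2 g/dL dated on the index date would be reported once as the patient's baseline hemoglobin and again as anemia on elranatamab. If the sample was drawn before the injection, the second entry is wrong.

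The protocol avoids this overlap elsewhere. Baseline neutropenia and hypercalcemia in Table 2, both with a laboratory criterion, end the day before the index date. So does baseline resource use in Table 3 and Section 9.7.5, although Section 9.2 words that window differently. At stake is whether the reported frequencies of three laboratory-supported events describe what happened on treatment or partly describe the state in which patients arrived. The same rule applies to the teclistamab cohort.

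**Working it through.** The protocol states no event rate or precision target that depends on this rule, so there is no figure to reproduce. The check applies the windows as written.

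**Inputs (day 0 = index date)**
- Baseline window: day −180 to day 0 (Table 2).
- Event window: day 0 to 14 days after the last dose (Table 3, Section 9.7.6; the 90-day version starts on the same day).
- Washout: day −30 to day −1 (Table 3 footnote, with Section 9.7.6 read as strictly before the index date).
- Revised rule for comparison: laboratory event window from day 1, washout from day −30 to day 0.

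**Result for patients whose only qualifying records are low hemoglobin values on the days shown**

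| Low hemoglobin on | In baseline window | Prevalent, as written | Incident, as written | Prevalent, revised | Incident, revised |
|---|---|---|---|---|---|
| day 0 only | yes | yes | yes | no | no |
| days −40 and 0 | yes | yes | yes | no | no |
| days −10 and 0 | yes | yes | no | no | no |
| day −10 only | yes | no | no | no | no |
| day 5 only | no | yes | yes | yes | yes |

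Rows 1 and 2 are scored incident although the protocol's own baseline value is already below the cut-off. Rows 3 and 4 differ in prevalence only because of the index-date sample. A patient low on day 0 and again on day 5 stays prevalent under either rule, so that patient adds nothing to any inflation of prevalence.

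**Which events are affected.** The double use needs a laboratory variable that appears in both tables. Hemoglobin/anemia, lymphocytes/lymphopenia and IgG/hypogammaglobulinemia qualify.

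**Scale.** Both formulas in Section 9.7.6 divide by the whole cohort. With the 56 patients in Section 9.5, one patient is 1/56 = 1.8 percentage points.

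For illustration only, suppose 27 of 56 patients are counted with anemia. This is near the 48.8% that Section 7 quotes from the phase 2 trial: 0.488 × 56 = 27.3. Let an assumed share of the 27 qualify solely through day 0. Intervals are exact 95% (Clopper-Pearson).

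| Assumed share | Patients removed | Prevalence under revised rule |
|---|---|---|
| 0% | 0 | 27/56 = 48.2% (34.7 to 62.0) |
| 10% | 3 | 24/56 = 42.9% (29.7 to 56.8) |
| 20% | 5 | 22/56 = 39.3% (26.5 to 53.2) |
| 30% | 8 | 19/56 = 33.9% (21.8 to 47.8) |

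The shares are assumptions; the protocol supplies none.

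**The case against.** The best defence is that prevalence is meant to include existing disease and that incidence, reported beside it, isolates new events. In the incidence formula, baseline could be read as the Table 2 laboratory window. That window includes the index date, so a low index-date value would not be incident. The outcomes are also exploratory and descriptive, and Section 9.7 rules out formal comparison between groups.

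Part of this stands. The formula is ambiguous, and the inclusive reading would protect incidence. But the sentence introducing it refers to events before the index date, and neither reading touches prevalence. Nor is prevalence simply inclusive of existing disease: a patient low only on day −1 is not counted, while one low only on day 0 is.

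Stronger readings are tempting, and the protocol does not support them:

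- **That all five laboratory-defined events are counted twice.** Potassium is not a Table 2 variable, so for hypokalaemia only the start of the window is at issue. The Table 3 neutropenia row shares the lymphocyte overlap only because it carries the lymphopenia definition, which is a separate error.
- **That every low index-date value inflates prevalence.** Only those with no later or other qualifying record in the window do.
- **That index-date samples are known to precede the dose.** The protocol is silent on draw time. Section 9.2.1 also allows a prescription claim to set the index date, so that date need not be the dosing day.
- **That the bias can be put at some number of points.** Any figure needs the frequency of index-date results, the share below the cut-off and the share without an earlier record. None is given, and Section 9.9 says laboratory values are often absent from claims data.

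**Conclusion.** The point holds for anemia, lymphopenia and hypogammaglobulinemia. Followed exactly, the stated windows turn an index-date baseline result into an on-treatment event. This is a stated rule that misclassifies, not a detail left for a later document.

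It biases prevalence upward to the extent that index-date samples precede dosing and are a patient's only qualifying record. It biases incidence upward to the extent that such patients also have a clear 30-day washout and baseline is read as strictly before the index date. The size is unknown. The 1.8 points per patient uses 56, which counts patients with an elranatamab claim at one data cut rather than the eligible cohort, and the step shrinks as the cohort grows. Because the outcomes are exploratory, this should be corrected, but it does not threaten the primary objectives.

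**What to change.** In Table 3 and Section 9.7.6:

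1. Start the event window for the laboratory criteria on the day after the index date.
2. Count index-date laboratory results as baseline, so that the washout for these criteria runs through the index date.
3. Define baseline in the incidence formula to match.
4. Keep the index date in the window for diagnosis-coded acute reactions such as CRS, ICANS, pyrexia and hypotension.
5. State how an index-date diagnosis code for anemia, lymphopenia or hypogammaglobulinemia is classified. Otherwise the code and laboratory parts of one variable have different start dates with no stated reason.

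The cost is a few sentences and a one-day change in the code. Results already delivered would need a rerun to stay comparable with later refreshes. There are two downsides. A true same-day drop after dosing is missed unless it recurs on a later sample. Where the index claim is a pharmacy claim that precedes dosing, the shift removes only part of the pre-dose results.

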Exploratory Obj 1	Hypophosphataemia ¹	Medical claim with an ICD-10 code in the IP, non-IP, or pharmacy setting for hypophosphatemia (dichotomous)	Index date to end of follow-up, where follow-up will be based on last dose of elranatamab (eg, 14 days after last recorded dose or 90 days after last recorded dose). See Section 9.7.6 for censoring criteria

Exploratory Obj 1	Hypokalaemia ¹	Medical claim with an ICD-10 code in the IP, non-IP, or pharmacy setting for hypokalemia or event in the lab table where potassium serum is < 3.0 mmol/L (dichotomous)	Index date to end of follow-up, where follow-up will be based on last dose of elranatamab (eg, 14 days after last recorded dose or 90 days after last recorded dose). See Section 9.7.6 for censoring criteria
Exploratory Obj 1	Hepatotoxicity ¹	Medical claim with an ICD-10 code in the IP, non-IP, or pharmacy setting for hepatotoxicity (dichotomous)	Index date to end of follow-up, where follow-up will be based on last dose of elranatamab (eg, 14 days after last recorded dose or 90 days after last recorded dose). See Section 9.7.5 for censoring criteria
Exploratory Obj 1	Renal failure ²	Medical claim with an ICD-10 code in the IP, non-IP, or pharmacy setting for renal failure (dichotomous)	Index date to end of follow-up, where follow-up will be based on last dose of elranatamab (eg, 14 days after last recorded dose or 90 days after last recorded dose). See Section 9.7.6 for censoring criteria
Exploratory Obj 1	Peripheral neuropathy ¹	Medical claim with an ICD-10 code in the IP, non-IP, or pharmacy setting for peripheral neuropathy (dichotomous)	Index date to end of follow-up, where follow-up will be based on last dose of elranatamab (eg, 14 days after last recorded dose or 90 days after last recorded dose). See Section 9.7.6 for censoring criteria

Exploratory Obj 1	Arthralgia ³	Medical claim with an ICD-10 code in the IP, non-IP, or pharmacy setting for arthralgia (dichotomous)	Index date to end of follow-up, where follow-up will be based on last dose of elranatamab (eg, 14 days after last recorded dose or 90 days after last recorded dose). See Section 9.7.6 for censoring criteria
Hematologic events			

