9.7.1. Descriptive Analysis

Dichotomous and categorical variables will be summarized by the number and percentage of patients in each category. Continuous variables will be described using mean (SD), median (IQR), minimum, and maximum. If applicable, the frequency and percentage of patients with missing data for each variable will be described. Furthermore, baseline characteristics will be assessed among elranatamab or teclistamab patients with and without a laboratory observation.

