9.9. Limitations of the Research Methods

While claims databases provide a wealth of comprehensive information to assess patients' demographic and clinical characteristics, a few limitations arise when using such databases. For instance, there may be misclassification of patient records due to provider coding practices (eg, using a diagnosis code as a rule-out criterion) or incorrect coding (eg, data entry errors). As such, the presence of a diagnosis code may not always accurately reflect the presence of disease for an individual patient. Such errors could affect patient eligibility and all variables used to assess treatment characteristics, HCRU, etc. Another potential issue that arises when using any database is generalizability. Oftentimes, the demographic makeup of the dataset is dependent on the providers that supply the information; if a dataset is heavily receiving data from one region of the US, then that might affect overall generalizability.

Databases that contain open and closed claims can offer information in real-time; they often are large in size and have a quick update cadence that allows for the immediate analysis of patient data. However, despite these strengths, there are some limitations associated with the use of open and closed claims. There is a risk of both patient and claim duplication, i.e., where the same patient shows up with a unique patient ID multiple times within the data. With a small cohort size, it may be hard to ascertain if such patients are unique to the dataset or if they are duplicates. Additionally, data providers such as Komodo are beholden to the suppliers of their claims data; therefore, if a data supplier withdraws and no replacement is found, then patient counts could drop across cuts.

Clinical events of interest defined by diagnosis codes may not capture the occurrence or intensity of the disease. Certain conditions, such as hematological toxicities, are often defined via specific cut-offs for certain lab values, which are not often provided in a claims data source. Therefore, ICD codes are used instead. Without lab values, the severity of the disease/grade cannot be determined. Therefore, patients whose AEs were not as severe in grade may not be captured.

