			G62.89, G61.9, G62.9, H46.3, M54.10, M54.18, M79.2, R20.0, R20.1, R20.2, R20.3, R20.8, R20.9	
Any infection	Baseline characteristic - Clinical	Claims data	An ICD-10 Diagnosis Code for any of the following types of infections. See the rows below for codes for each infection type. COVID-19, Adenoviral pneumonia, Cytomegaloviral pneumonitis, Other Pneumonia, Upper respiratory tract infection, Sepsis, Cytomegaloviral infection, PJP, Hepatitis C, Hepatitis B, Other infectious hepatitis, Helicobacter pylori, Candida esophagitis, Urinary tract infection	N/A
Use of intravenous anti-infective	Baseline characteristic - Clinical	Claims data	See “Antivirals,” “Antibiotics,” and “Antifungals” and where service category = injection/infusion drugs or where route = injectable or route array has injectable in it OR HCPCS/CPT codes that indicate IV administration of an anti-infective	N/A
Absolute neutrophil count (for Neutropenia)	Baseline characteristic - Clinical, AE	Claims data	White blood cell count x the percentage of neutrophils White blood cell count: Results_value in the lab results table where the result_abbrev is wbc and result_units are thousand per μ L Percent Neutrophil: Results_value in the lab results table where the result_abbrev is neutrophils percent and result_units are percent White blood cell count and percent neutrophil results must occur on the same day	Severe Chronic Neutropenia International Registry
Neutropenia	Baseline characteristic - Clinical, AE	Claims data	ICD-10 Diagnosis: D70.x or Absolute neutrophil count < 1500 cells per μ L	Kim et al. (2022) Lustberg et al. (2012)

PFIZER CONFIDENTIAL

Redacted

Hypercalcemia	Baseline characteristic - Clinical	Claims data	ICD-10 Diagnosis: E83.52 or value in the GDD table where test is hypercalcemia and result_units are mg/dL and result_value is > 11.5	Kumi et al. (2024) CTCAE v6 (2020)
Hepatotoxicity	Baseline characteristic - Clinical, AE	Claims data	ICD-10 Diagnosis: K71.x	Banerjee et al. (2023)
Amyloidosis	Baseline characteristic - Clinical	Claims data	ICD-10 Diagnosis: E85.4x, E85.8x, E85.9x	Quock et al. (2018)
Hypertension	Baseline characteristic - Clinical	Claims data	ICD-10 Diagnosis: I10x-I15x	Angier et al. (2019)
Extramedullary plasmacytoma	Baseline characteristic - Clinical	Claims data	ICD-10 Diagnosis: C90.2x	Ellington et al. (2021)
CCI score	Baseline characteristic - Clinical	Claims data	See components below	Glasheen et al. (2019)

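### Five adverse events are counted on a diagnosis code or a lab value but divided by the whole cohort, so their percentages depend partly on how many patients have lab data

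*Protocol*

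**What the plan says.** In Table 3 (section 9.3), anemia is met by a claim code "for anemia or event in the lab table where hemoglobin is <10g/dL (dichotomous"). The lymphopenia row reads "lymphopenia or event in the lab table where lymphocyte count is < 1,000 per uL (dichotomous"). The other two such rows are "hypogammaglobulinemia or event in the lab table where IGG value is" at or below 400 mg/dL, and "hypokalemia or event in the lab table where potassium serum is < 3.0 mmol/L (dichotomous").

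The neutropenia row of Table 3 repeats the lymphopenia text. Annex 2 defines neutropenia by a code or an absolute neutrophil count below 1,500 cells per µL, built from two results: "White blood cell count and percent neutrophil results must occur on the same day". On either reading the event depends partly on lab data.

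Section 9.7.6 gives formulas for prevalence and incidence, and both have the denominator "Total number of patients in the cohort". Footnote 1 of Table 3 applies a 30-day washout to all five events in the incidence analysis.

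On lab availability, section 9.7.1 says that "baseline characteristics will be assessed among elranatamab or teclistamab patients with and without a laboratory observation". The limitations in section 9.9, writing of toxicities normally defined by lab cut-offs, say: "Therefore, ICD codes are used instead. Without lab values, the severity of the disease/grade cannot be determined".

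**The concern.** There are two routes to an event, and one of them is closed to patients with no lab data. Such a patient, if also without a code, enters the denominator as event-free. The result is neither a claims-based rate nor a lab-based rate but a mixture, weighted by the share of patients who have results. That share has nothing to do with tolerability.

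Describing these rates is the purpose of Exploratory Objective 1, so a shortfall in the rate matters even without a comparison. The same tables will also be produced for teclistamab and at successive refreshes, where readers will set the numbers side by side. The planned 95% confidence intervals cover sampling error only and would not show the shortfall. A reader who relies on section 9.9 would take the rates to be code-only.

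**Working it through.** The protocol states no expected event rate in this cohort and no lab coverage, so there is no planned figure to reproduce. The check has three parts.

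**1. Does any text link the denominator to lab availability?** Table 3 and Annex 2 open the lab route for five events. Section 9.7.6 uses the whole cohort for all events. The split in section 9.7.1 covers baseline characteristics only. The sentence before Table 3 promises, where applicable, counts of missing data for each variable, but it leaves the denominator unchanged. No adverse-event estimate is restricted to, or stratified by, patients with lab data.

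**2. Illustration of the size.** Let

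- p = true event rate. I use 48.8%, the anemia rate (and also the neutropenia rate) that section 7 cites from the phase 2 trial;
- s = share of true events that produce a code (assumed 0.5 or 0.7);
- c = share of patients with lab data (assumed 20% or 60%).

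Assume that labs find every event in covered patients and that coverage is independent of risk. Then

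expected reported rate = p × [s + (1 − s) × c]

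| Coverage c | s = 0.5 | s = 0.7 |
|---|---|---|
| 20% | 0.488 × (0.5 + 0.5 × 0.2) = 29.3% | 0.488 × (0.7 + 0.3 × 0.2) = 37.1% |
| 60% | 0.488 × (0.5 + 0.5 × 0.6) = 39.0% | 0.488 × (0.7 + 0.3 × 0.6) = 42.9% |

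The shift is p × (1 − s) × change in c:

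- s = 0.5: 0.488 × 0.5 × 0.4 = 9.8 points
- s = 0.7: 0.488 × 0.3 × 0.4 = 5.9 points

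If labs find only a fraction d of the uncoded events, the shift is multiplied by d. At d = 0.5 the two figures halve to 4.9 and 2.9 points.

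Under the same assumptions (d = 1), the code-only rate in the whole cohort is p × s = 0.488 × 0.5 = 24.4%, or 0.488 × 0.7 = 34.2%, at any coverage. The code-or-lab rate among patients with lab data is 48.8% at any coverage. Neither moves with c.

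**3. Incidence.** A pre-index low value can remove a patient from the incident count by the lab route only if a result falls in the 30-day washout. A patient with a long-standing low value, no code and no result in those 30 days becomes an incident case at the first low value after index. Lab coverage before index therefore lowers incidence, while coverage after index raises it. The net direction cannot be told from the protocol.

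**The case against.** The strongest reply is that the size is wholly assumed. That stands. The protocol gives no coverage and no code sensitivity. The 48.8% is a trial adverse-event rate quoted without a hemoglobin cut-off, whereas Table 3 counts only values below 10 g/dL that reach the lab table. Perfect lab detection therefore pushes the illustrated shifts upwards.

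Second, the objective is exploratory, and section 9.7 rules out formal comparison between groups. A reader might infer that differences between elranatamab and teclistamab, or between refreshes, will be artefacts of lab coverage. The protocol does not support that, because nothing in it shows that coverage differs between cohorts or data cuts. What stands is that coverage affects the level of each rate.

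Third, under-ascertainment is disclosed in general terms: section 9.9 warns that milder events may be missed. Detailed stratification could also sit in an SAP or in table shells that are not shown. But the denominator is fixed in the protocol's own formulas, and the general warning comes with a statement that lab values are not used.

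Fourth, restricting to tested patients brings its own selection, since sicker or longer-followed patients are tested more. That is a good reason not to insist that the pooled percentage be dropped.

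Finally, a reader might infer that Version 2.0 introduced the lab criteria for these events. The amendment log does not list that among the Table 3 changes. It records lab additions for Table 2 and the annex, so the history should be left open.

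**Conclusion.** The point holds as a matter of ascertainment. For these five events the protocol combines a code-or-lab numerator with a whole-cohort denominator, while accepting that only some patients have lab data. The pooled prevalence therefore depends partly on lab coverage, and the incidence also depends on who has a result in the washout. Section 9.9 contradicts Table 3 and Annex 2 and leaves the mixture undisclosed.

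The size is unknown. The shifts of about 10 and 6 points are illustrations that rest on a 48.8% true rate, code sensitivity of 0.5 or 0.7, perfect lab detection, coverage independent of risk, and a move from 20% to 60% coverage. They are not estimates for this database. Because the analysis is exploratory and descriptive, this is a worthwhile and cheap improvement and does not invalidate the study.

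**What to change.** In section 9.7.6, for anemia, neutropenia, lymphopenia, hypogammaglobulinemia and hypokalaemia, report:

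- (a) the code-only estimate in the whole cohort;
- (b) the code-or-lab estimate among patients with at least one result for that analyte in the risk window, with the number tested and, for incidence, the number with a result in the washout.

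If the pooled code-or-lab percentage over the whole cohort is kept, label it as mixed ascertainment. Correct the sentence in section 9.9 that says codes are used instead of lab values. Before (b) can be programmed, reconcile the Table 3 neutropenia row with Annex 2. Reconcile also the lymphocyte cut-off, which is below 1,000 per µL in Table 3 and below 1.5 thousand per µL in Annex 2.

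The cost is protocol wording and a few table rows from data already held. Estimate (b) will have wider intervals: with the 56 elranatamab claimants reported in section 9.5 and an assumed 20% coverage, it would rest on about 11 patients (56 × 0.2 = 11.2). It may also over-represent patients who are tested more because they are sicker or followed longer, so it should be read beside (a).
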